Following the identification of quercetin-3-rutinoside and related flavonoids as potent inhibitors of PDI, we performed laser- induced vascular injury experiments in mice and observed inhibition of platelet thrombus formation and fibrin generation following intravenous and oral administration. A modest dose of oral quercetin (5 mg/kg) yielded a ~50% reduction in platelet accumulation and fibrin generation in mice. The PDI-specific nature of this interaction is confirmed by addition of recombinant human PDI to neutralize quercetin activity.

Quercetin as an anticoagulant in humans

In order to evaluate the potential antithrombotic activity of quercetin in humans, d-dimer levels were measured in plasma samples following administration of oral quercetin. In this previously published clinical trial conducted at University of Utah, study subjects received oral quercetin (365 mg twice daily) for 28 days. Eligible patients were hypertensive and excluded for a history of cardiovascular events, diabetes, renal disease, obesity, or active smoking. In four patients with baseline elevations in d-dimer (>500 ng/ml) there was a significant decrease in mean plasma d-dimer levels compared with baseline (1198 vs. 462 ng/ml, P=0.056). No change in d-dimer levels was observed in patients (N=20) with normal baseline concentrations (174 vs. 184 ng/ml, P=0.97).

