Microparticles will be isolated from PFP and PDI activity on the surface of plasma microparticles will be measured with a fluorescent substrate (dieosin glutathione disulfide or di-E-GSSG) per previously described methods (Raturi et al Biochimica et Biophysica Acta 2008;1778:2790-2796.

Additional hemostasis-related assays such as microparticle and tissue factor activity will be performed using PFP.

В.	Statistical Considerations

a. **Sample Size Justification:** A total of 40 healthy individuals will be enrolled in the trial. Data collected from the pharmacokinetic analysis will be used to identify the formulation of study drug, either isoquercetin or quercetin with or without ascorbic acid. Ten patients per group is the minimum number necessary to establish a difference in values of pharmacologic variables (e.g. Cmax or AUC) of at least one standard deviation of magnitude with a 0.05 level of significance using a paired two-tailed test of log-transformed values. Although this study may be technically underpowered to detect small differences, a clinically significant difference between the relative bioavailability among the four formulations should be readily apparent. If a subject chooses not to participate in the second part of the study (i.e. quercetin in combination with ascorbic acid and niacin) then alternative subjects will be recruited to complete the second PK/PD analysis.

For the cohort with antiphospholipid antibodies or myeloproliferative disorder, we plan to enroll 20 patients (approximately 10 in each arm). The null hypothesis is there is no difference in thrombin-induced thrombin generation measured at 0 and 4 hours. The sample size calculation is based on preliminary data demonstrating that the mean decrease in thrombin generation before and after isoquercetin was -54% with a

standard deviation of mean % difference of .41 in healthy individuals. Accordingly, using a paired t-test analysis for time 0 and 4 hours with a 2-sided alpha of 0.05, the power of the study is 95.8

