b. **Data Analysis:** The concentration of quercetin in plasma will be determined by liquid chromatography and mass spectrometry in collaboration. Analysis will include elimination half-life, peak concentration, and area under the curve. We will also evaluate an experiment assay to monitor PDI inhibition in plasma using a dieosin glutathione disulfide (di-E-GSSG) to liberate a self-quenching N-terminal GSSG residue following cleavage of a disulfide bond. There is a planned comparison of peak PDI inhibition for the different groups and correlation with serum quercetin levels. Statistical analysis will be performed in collaboration with [name] and [name] at DFCI.

C. Subject Selection

Inclusion Criteria

- 1. Subject is willing to participate and provide informed consent
- 2. Subject is considered reliable and capable of adhering to the protocol per the judgment of the Investigator
- 3. Subjects in group D must exhibit good organ reserves (within prior 4 weeks) defined as:
- a. Estimated GFR >35 (formula),
- b. Platelet count >65 K/uL,
- c. Hemoglobin >10.5 grams/dL
- d. Total bilirubin <2.0 mg/dL
- 4. Minimum age 18 years old
- 5. Body mass index (BMI) between 18 and 35 kg/m2
- 6. For cohort D (antiphospholipid antibodies or myeloproliferative disorder)

a. Subjects in group D with antiphospholipid antibodies must have at least one positive antiphospholipid antibody within the last 8 weeks and/or previous confirmed antibodies (2 or more occasions at least 12 weeks apart) :

i. Positive lupus anticoagulant

- ii. anticardiolipin antibody IgM or IgG (>40U GPL)
- iii. anti- β 2 Glycoprotein1 antibody titer (>35 units)

b. Subjects in cohort D with myeloproliferative disorder must have confirmed diagnosis of essential thrombocythemia or polycythemia vera through bone marrow biopsy or molecular testing.

Exclusion Criteria

1. Pregnant. If female of child-bearing age, negative urinary pregnancy test prior to dosing of quercetin or isoquercetin

2. No history of malabsorptive gastrointenstinal disorder

3. Currently taking, warfarin, low-molecular weight heparin or other anticoagulants (such as direct thrombin inhibitors or factor X inhibitors)

- 4. Prescribed niacin for hyperlipidemia
- 5. Known HIV

6. History of sensitivity or intolerance to flavonoids, niacin or ascorbic acid

7. May not have uncontrolled intercurrent illness including, but not limited to ongoing or

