active infection, hepatitis, symptomatic congestive heart failure, unstable angina pectoris or cardiac arrhythmia

Foods containing quercetin that study subjects will be asked to avoid for 72 hours before the first dose of study drug (and between the 8 and 24 hour blood samples) include:

Vegetables: beans (green, yellow, snap), broccoli, capers, kale, lettuce, onion, peppers (hot, sweet, green, jalapeno), red cabbage, spinach, tomato

Fruit: apples, apricot, blackberries, blueberries, cherry, cranberry, grapes, lemon, oranges, plums, raspberries, strawberry.

Other: chocolate/cocoa, honey, tea, wine

B4. POSSIBLE BENEFITS

This study will not directly benefit the study subjects. Pharmacokinetic and pharmacodynamics studies of quercetin will facilitate the conduct of clinical trials of quercetin to treat prothrombotic conditions.

B5. POSSIBLE RISKS AND ANALYSIS OF RISK/BENEFIT RATIO

Quercetin is considered safe without significant toxicities and Quercegen Pharma received GRAS designation from the FDA for their quercetin formulation (Inventory Number GRN 341). Quercetin has been used in numerous clinical studies with a long established history of safety. Quercetin or isoquercetin (>99.5% purity) alone or in combination with ascorbic acid and niacin will be provided by Quercegen Pharma (Sudbury, MA) which adheres to Good Manufacturing Practice guidelines and previously provided study drug for randomized clinical trials conducted in the United States. As a common dietary flavonoid, quercetin has been evaluated in a number of clinical trials with different endpoints. Quercetin may lower blood pressure slightly as was demonstrated in a randomized trial of 43 individuals treated with quercetin 365 mg twice daily for 28 days. Both systolic and diastolic blood pressure were modestly lower at 28 days in the guercetin treated patients (7 mm Hg and 5 mm Hg, respectively) although this effect was not observed in a other studies. No significant change was observed with lipid profiles or serum glucose. In a randomized trial of 1002 outpatients treated with oral guercetin 500mg or 1000 mg daily for 3 months to prevent upper respiratory infections, there were no significant adverse events reported. In a phase I study where guercetin was administered intravenously at doses greater than 2000 mg, there was evidence of nephrotoxicity in several patients.

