Healthy subjects will undergo a venipuncture and placement of an IV with subsequent draw of 80cc over the course of 24 hours. Antiphospholipid subjects will undergo a venipuncture and

placement of an IV with subsequent draw of 40cc over the course of 4 hours. Risks associated with IV placement and lab draws include pain, ecchymosis, and rarely superficial thrombophlebitis. Some individuals can experience a vaso-vagal reaction to venipuncture.

B6. RECRUITMENT AND CONSENT PROCEDURES Recruitment

Subjects will be recruited at the medical center. Flyers will be posted at different locations at BIDMC and Center for Life Sciences Building (CLS) requesting healthy subjects interested in participating in a the study. Investigators will discuss with the protocol with potential subjects and provide a consent form describing this study for the subjects to review. Recruitment for Cohort D will include discussion with rheumatology and hematology staff of potentially eligible study subjects. We will also access BIDMC CQ2 database to identify eligible participants who have been diagnosed with an antiphospholipid antibodies. Following identification of potentially eligible study subject, physician or nurse will contact subject and discuss whether they may be interested in participating. Based on interest, will be evaluated in clinic and will review consent and eligible criteria.

Following consent, inclusion criteria will be reviewed to confirm eligibility for study participation using a checklist that will be signed and dated by the Investigator confirming eligibility. The subjects will be given list of flavonoid-rich foods to avoid 72 hours prior to scheduled participation.

Consent

The formal consent of a participant, using the IRB approved consent form, will be obtained before the participant is involved in any study-related procedure. The participant will be given a copy of the signed and dated consent document. The original signed copy of the consent document will be retained in a research file and documentation of consent will be placed in the medical record.

Subject Protection

All participants receiving study agents will be evaluated for safety. The safety parameters include spontaneous reports of adverse events reported to the investigator by participants. All toxicities encountered during the study will be evaluated according to the NCI criteria (CTCAE 4.0). Life-threatening toxicities will be reported immediately to [name] and IRB.

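### Bleeding follows from the drug's intended action, but B5 does not name it as a possible drug effect and the only stated means of capture is spontaneous reporting

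*Combined protocol and SAP*

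**What the plan says.** **Rationale.** B2 presents the drug as an antithrombotic. A modest oral dose "yielded a ~50% reduction in platelet accumulation and fibrin generation in mice", and swallowing onion soup or a quercetin glucoside reduced platelet aggregation measured ex vivo. The sample-size text (B3.B.a) states for healthy people that "the mean decrease in thrombin generation before and after isoquercetin was -54" per cent, with a "standard deviation of mean % difference of .41 in healthy individuals".

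**Risk section.** B5 opens with "Quercetin is considered safe without significant toxicities". The drug effects it goes on to describe are a small blood-pressure reduction and nephrotoxicity after intravenous doses above 2000 mg. Ecchymosis is listed, but only as a consequence of IV placement and blood draws.

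**Entry.** B3.C excludes anticoagulant users in every group. Group D must also meet blood-count floors ("Platelet count >65 K/uL" and hemoglobin above 10.5 g/dL). Groups A, B, C and E have no blood-count requirement. No criterion mentions current bleeding, bleeding history or a bleeding disorder.

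**Safety capture.** B6, Subject Protection: "The safety parameters include spontaneous reports of adverse events reported to the investigator by participants". Toxicities are graded by CTCAE 4.0. Under the study procedures in B3.A, Group D may leave after the 4-hour draw. The other groups stay until the 8-hour draw and return at 24 hours.

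**The concern.** The harm most directly implied by the proposed mechanism is the one that the risk section leaves out and that nobody is instructed to ask about. The plan measures the laboratory side (thrombin generation, platelet aggregation, other hemostasis assays) but has no solicited clinical counterpart.

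Two kinds of loss are possible. A participant may not volunteer a nosebleed or a bruise. Or a bruise may be reported and then attributed to the needle, which is the only cause of bruising that B5 offers. That attribution is easy in this study: healthy participants are sampled at eight time points and may choose serial venipuncture.

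B4 says the study is meant to facilitate trials in prothrombotic conditions. A record with no bleeding reports would carry little information into that planning if bleeding was never asked about.

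**Working it through.** **1. Is the antithrombotic effect a working assumption of the plan?** Inputs from B3.B.a: mean fall 54%, SD 0.41, paired t-test, two-sided alpha 0.05, about 10 patients per arm of Group D.

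- Standardized effect: d = 0.54 / 0.41 = 1.317.
- Noncentrality at n = 10: 1.317 × √10 = 4.165, with 9 degrees of freedom.
- Exact noncentral-t power: 95.83%.

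This reproduces the plan's figure: "using a paired t-test analysis for time 0 and 4 hours with a 2-sided alpha of 0.05, the power of the study is 95.8" (per cent). With all 20 patients in one test, power would be 99.98%, so the stated value belongs to one arm of 10. The calculation is not in dispute. It shows that Group D was sized on a large reduction in thrombin generation.

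**2. The sections side by side.**

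| Question | What the protocol provides | What it does not provide |
|---|---|---|
| Named as a drug risk (B5)? | Blood pressure; intravenous nephrotoxicity | Bleeding or bruising from the drug |
| Bruising mentioned (B5)? | Yes, from IV placement and draws | Any way to separate it from a drug effect |
| Entry, all groups (B3.C)? | Anticoagulants excluded | Bleeding history or bleeding disorder |
| Entry, Group D (B3.C)? | Platelet and hemoglobin floors | Same gap as above |
| Entry, Groups A, B, C, E (B3.C)? | No blood-count requirement | Same gap as above |
| Capture (B6)? | Spontaneous reports, CTCAE 4.0 grading | A solicited bleeding question |
| Last contact described, Group D (B3.A)? | 4 hours | Anything later |

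**3. What would no reports tell us?** With zero events in n participants and complete ascertainment, the one-sided 95% upper limit on the true rate is 1 − 0.05^(1/n).

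- Group D, n = 20: 1 − 0.05^(1/20) = 13.9%.
- Healthy groups, n = 40 (B3.B.a): 1 − 0.05^(1/40) = 7.2%.
- All, n = 60: 1 − 0.05^(1/60) = 4.9%.

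If only a fraction r of participants with an event report it, zero reports bound the product of r and the true rate, so each limit is divided by r. The documents give no value for r. As an assumed range:

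| r | Group D limit | Healthy limit |
|---|---|---|
| 1 | 13.9% | 7.2% |
| 0.75 | 18.5% | 9.6% |
| 0.5 | 27.8% | 14.4% |

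These are limits on what could be ruled out, not estimates of how often bleeding will occur. A fixed question raises r. It does not change n, so even at best the reassurance is modest.

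**The case against.** The strongest case against is that the plan is not blind to hemostatic risk, and that what remains is wording in a small, short study.

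- **Entry.** A reader might infer that bleeding is not considered at entry at all. The documents do not support that. Anticoagulants are barred throughout and Group D has two blood-count floors. The exclusion for uncontrolled intercurrent illness is open-ended and could cover an active bleed. B8 says relevant medical history is taken for eligibility, and B6 requires an investigator-signed checklist. This stands. What is missing is an explicit statement about bleeding history.
- **Capture.** A reader might infer that bleeding would not be measured. B6 says that safety parameters *include* spontaneous reports, which is not the same as *only*, and a reported bleed would be graded. Participants are also seen at the center for hours after dosing. This stands in part: nothing beyond spontaneous reporting is specified, so active questioning cannot be assumed.
- **Evidence of safety.** B5 cites 1002 outpatients who took oral quercetin 500 or 1000 mg daily for 3 months without significant adverse events, and exposure here is a single dose per visit. This tempers the concern. That study concerned quercetin, however, while most groups here receive isoquercetin.
- **Size.** It is tempting to read the 54% mean and 0.41 SD as the share of patients with an extreme fall in thrombin generation, and so as a bleeding risk. The normal model behind such a figure puts 1 − Φ((1.00 − 0.54) / 0.41) = 1 − Φ(1.12) = 13% of patients beyond a 100% fall, which is impossible. No document links any thrombin-generation value to clinical bleeding.
- **Consent.** A reader might infer that participants are not told of the risk. The consent pages are not in the public file, so this cannot be judged.
- **Purpose.** No tolerability endpoint or claim is planned, so misuse of a clean record is a possibility, not a certainty.

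**Conclusion.** The point holds in limited form. The protocol's rationale is reduced platelet and fibrin deposition, yet B5 does not name bleeding as a possible drug effect, entry safeguards are partial and silent on bleeding history, and the only stated capture is passive. A mechanism-based bleed or bruise may therefore be missed or attributed to the needle.

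It does not follow that bleeding is likely, that it is wholly unscreened, or that it would go unrecorded once reported. The documents give no bleeding rate and no reporting rate, so the size of the harm cannot be estimated. The one firm quantity is that zero events in Group D would exclude only rates above 13.9%, and higher ones if reporting is incomplete; this assumes 20 evaluable patients. The power calculation and endpoints are untouched. This is a low-cost safety improvement, not a flaw in the main analysis.

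**What to change.** 1. **B6.** Add one fixed bleeding and bruising question at post-dose contacts that already take place: 4 hours in Group D; 4, 8 and 24 hours in Groups A, B, C and E. Record yes or no with CTCAE grade, and separate IV-site bruising from bleeding or bruising elsewhere.
2. **B3.B.b.** Tabulate the answers by group and dose. Count participants as well as visits, since some healthy participants may attend twice.
3. **B5.** Name bleeding as a possible risk that follows from the mechanism, and confirm that the consent text matches.
4. **B3.C.** Ask the sponsor to decide, and state, whether current bleeding or a known bleeding disorder is an eligibility matter.

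The cost is a few lines of protocol text, one form item and one table, with no new visit. The downside is a few extra mild bruising entries. A 4-hour question in Group D would still miss later events, and the report should say so.
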